### REASON(S) FOR CHANGE(S):

In Section 13.3, Page 19 of the Protocol, the Randomization Left/Right Balance needs to be corrected due to a typographical error about randomization replacements.

In Section 15.4 (Anticipated Reactions), Page 27 of the Protocol, Page 8 (Risks) of the Informed Consent Form as well as Page 7 (Risks) of the Informed Consent Form - Neutralization Assay, the anticipated reactions need to be updated to include one more anticipated reaction.

### CHANGE(S):

In Section 13.3 on Page 19 of the Protocol, for the Left/Right Balance, the statement "The application will be randomized so that each treatment is used on an equal number of left and right sides of the body with the exception of replacement subjects." will be changed to, "The application will be randomized so that each treatment is used on an equal number of left and right sides of the body."

On page 2 of Appendix 1, the procedure for ZuraPrep™ Vehicle (Negative Control) [REDACTED]

[REDACTED] This will be changed to: [REDACTED]

In Section 15.4 (Anticipated Reactions), Page 27 of the Protocol, and on Page 8 of the Informed Consent Form as well as Page 7 of the Informed Consent Form - Neutralization Assay, in the Risks sections, folliculitis will be added as an anticipated reaction from clipping. For the Informed Consent Form, and new version of the Form will be created (Version 02) and approved by the GIRB. Clipping has already occurred for the neutralization, therefore, a subject letter will be signed by subjects who clipped in the neutralization – the letter will be approved by the GIRB. See attached letter for neutralization subjects, and version 02 of the Informed Consent Form.

## PROTOCOL AMENDMENT FORM

DATE: 03/30/2017

PROTOCOL NUMBER: 150316-103

SPONSOR: Zurex Pharma, Inc.

PROTOCOL TITLE: PIVOTAL CLINICAL EVALUATION OF [REDACTED] A PATIENT PREOPERATIVE SKIN PREPARATION (Sponsor Project Number: ZX-ZP-0074)

**REASON(S) FOR CHANGE(S):** The inclusion criterion regarding baseline screening results have been expanded to allow subjects to proceed to Treatment Day if they have passing Screening Day baseline counts on the left and right sides of the abdomen and /or the left and right sides of the groin due to recruitment challenges around subjects meeting the minimum screening baseline requirements in the abdomen.

Section 11.3, Criteria for Inclusion, second bullet point (page 17) will state the following:

Have Screening Day baseline counts of at least  $1.0 \times 10^3$  CFU/cm^2 per abdominal site (left and right) and/or at least  $1.0 \times 10^5$  CFU/cm^2 per groin site (left and right).

Section 13.4, Baseline-Screening Sampling: The third paragraph will state the following:

Baseline criteria for qualification for the test period are  $3.0 \log_{10}$  CFU/cm^2 from the skin of the abdomen, and  $5.0 \log_{10}$  CFU/cm^2 on the skin on the groin. Subjects may qualify on either one or both anatomical site(s) and be admitted into testing for those anatomical site(s) only, or one if the sample size minimums have been met for an anatomical region. If more subjects qualify for treatment than can be treated in a given time period, preferential admittance into the treatment phase will be given to subjects qualifying in both the abdominal and inguinal test areas, followed by subjects who pass abdomen only. Subjects that qualify may be moved to a future group for testing the following week without having to re-qualify (clip or go through screening baseline again). If subjects that qualify need to move to a future group later than the following week, the subjects will be required to re-qualify (clip if needed and go through screening baseline). Subjects who do not qualify may be allowed to be screened again at the discretion of the Principal Investigator.

**PROTOCOL AMENDMENT FORM**

**DATE:** 03/30/2017

**PROTOCOL NUMBER:** 150316-103

PROTOCOL AMENDMENT FORM

DATE: 04/06/2017

PROTOCOL NUMBER: 150316-103

SPONSOR: Zurex Pharma, Inc.

PROTOCOL TITLE: PIVOTAL CLINICAL EVALUATION OF [REDACTED] A PATIENT PREOPERATIVE SKIN PREPARATION (Sponsor Project Number: ZX-ZP-0074)

REASON(S) FOR CHANGE(S): To update and clarify the randomization section of the protocol as a result of the changes implemented in Protocol Amendment Form 03 (screening day baseline criteria expansion).

[REDACTED]  
In Section 13.3, Randomization, under "Treatment Balance", the sentence:

"Each subject will receive two different treatments, one on the right side of the body and one on the left."

Will be changed to:

"Each subject will receive two different treatments *per anatomical site* (abdomen or groin), one on the left and one on the right. A subject that has qualifying screening baselines on both anatomical sites may receive up to 3 different treatments."

[REDACTED]  
STUDY DIRECTOR / PRINCIPAL INVESTIGATOR

04/06/17

DATE

## PROTOCOL AMENDMENT FORM

DATE: 08/29/2017

PROTOCOL NUMBER: 150316-103

SPONSOR: Zurex Pharma, Inc.

PROTOCOL TITLE: PIVOTAL CLINICAL EVALUATION OF [REDACTED], A PATIENT PREOPERATIVE SKIN PREPARATION (Sponsor Project Number: ZX-ZP-0074)

REASON FOR CHANGE(S): This amendment is issued after the completion of testing to add additional efficacy criteria in the below sections to the study protocol in accordance with [REDACTED] recommendations by the Division of Nonprescription Drug Products of the Food and Drug Administration (FDA) [REDACTED]

CHANGE(S): The following paragraph is added to the end of *Section 7.1 Primary Analysis* of the protocol:

Additionally, as recommended by FDA, product effectiveness will be measured using the average treatment effects (ATE). The ATE will be estimated from a linear regression of post-treatment bacterial count ( $\log_{10}$  scale) at 10 minutes on the additive effect of a treatment indicator and the baseline or pretreatment measurement ( $\log_{10}$  scale). To show effectiveness, the test product will be 1) non-inferior to ChloraPrep® with a 0.5 margin ( $\log_{10}$  scale, upper bound of 95% confidence interval of the difference in ATE values  $\leq 0.5$ ) and 2) superior to the vehicle control by a margin of 1.2 ( $\log_{10}$  scale, lower bound of 95% confidence interval of the difference in ATE values  $\geq 1.2$ ).

*Section 16.2 Efficacy (Primary) Analyses* title is revised to remove *(Primary)* for accuracy, to *Efficacy Analyses*.

*Section 7.2 Secondary Analysis* is revised (additions underlined for clarity):

Responder rates, ATE values, and differences in ATE values at 30 seconds will be calculated identically to the 10-minute responder rates and ATE values. At 6 hours a site is considered a responder if it is below baseline; otherwise, 6-hour responder rates will be calculated identically to the 10-minute responder rates. The secondary efficacy goals are to have the 95% confidence intervals for the responder rates to be greater than or equal to 70%. Log10 reductions from baseline will also be calculated for all post-prep samples. The non-inferiority and superiority goals for ATE values are identical to those at 10 minutes.

The following paragraphs are added prior to the last paragraph in *Section 16.2 Efficacy Analyses* of the protocol:

Average Treatment Effect (ATE) will be estimated from a linear regression of post-treatment bacterial count ( $\log_{10}$  scale) on the additive effect of a treatment indicator and the baseline or pretreatment measurement ( $\log_{10}$  scale). ATE will be calculated for the 10-minute samples separately for each product and each body area. [REDACTED]

The ATEs will be compared as follows:

- a. ZuraPrep™ will be compared to the ChloraPrep®. To show effectiveness, ZuraPrep™ should be non-inferior to ChloraPrep® with a 0.5 margin. Specifically, the upper bound of the 95% confidence interval of the ATE of ChloraPrep® minus the ATE of ZuraPrep™ should be less than or equal to 0.5.
- b. ZuraPrep™ will be compared to ZuraPrep™ vehicle. To show effectiveness, ZuraPrep™ should be superior to ZuraPrep™ vehicle by a 1.2 margin. Specifically, the lower bound of the 95% confidence interval of the ATE of ZuraPrep™ minus the ATE of ZuraPrep™ vehicle should be greater than or equal to 1.2.

The same ATE calculations will be performed for the 30-second time point, but the results are for informational purposes only.

PROTOCOL AMENDMENT FORM

DATE: 08/29/2017

PROTOCOL NUMBER: 150316-103

APPROVALS:

[REDACTED]

  
STUDY DIRECTOR / PRINCIPAL INVESTIGATOR

08/29/17

DATE

[REDACTED]

REVIEWED BY:

[REDACTED]

[REDACTED]

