## 11.0 SUBJECT SELECTION

### 11.1 Number of Subjects

A sufficient number of subjects at least 18 years of age will be screened, meet baseline criteria, and be entered into testing in order to complete a total of 704 abdominal site evaluations and 704 groin site evaluations (minimum of 352 completed subjects). ZuraPrep™ and ChloraPrep® will each be paired and evaluated with a sample size of at least 288 subjects. The negative control (ZuraPrep™ Vehicle) will be paired and evaluated with ZuraPrep™ and with ChloraPrep®, with a sample size of at least 32 subjects for each pairing. A total of at least 320 inguinal and abdomen sites will be treated with ZuraPrep™ and ChloraPrep®, and at least 64 inguinal and abdomen sites will be treated with the negative control.

[figure not shown]

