### **13.9 Data Handling**

The estimated  $\log_{10}$  number of viable microorganisms per  $\text{cm}^2$  recovered from each sample site will be designated the "R-value."

To convert the volumetric measure of the sample into the number of colony-forming units per square centimeter ( $\text{cm}^2$ ), the following formula will be employed:

$$R = \log_{10} \left[ \frac{F \left( \frac{\sum c_i}{n} \right) 10^{-D}}{A} \right]$$

Where:

$R$  = the average colony-forming unit count in  $\log_{10}$  scale per  $\text{cm}^2$  of sampling surface

$F$  = total number of mL of stripping fluid added to the sampling cylinder; in this study,  $F =$  [REDACTED]

$\frac{\sum c_i}{n}$  = average of the duplicate colony counts used for each sample collected

$D$  = dilution factor of the plate counts

$A$  = inside area of the cylinder in  $\text{cm}^2$ ; in this study,  $A =$  [REDACTED]

**NOTE:** The reason that a  $\log_{10}$  transformation will be performed on the collected data is to obtain a linear scale. A linear scale, more appropriately a  $\log_{10}$  linear scale, is a basic requirement of the statistical models used in this study.

If colonies on one of the plates is uncountable, the count from the remaining plate will be used.

Colony counts of 0 will be set to 0.5 for further calculation purposes. The average for duplicate plates each containing 0 CFU's would result in an average of 0.5 CFU's further used for calculating the R Value.

Data collected from subjects with low or high test-day baseline counts on an anatomical test site ( $< 3.0 /> 5.5 \log_{10}$  CFU/ $\text{cm}^2$  from the skin of the abdomen, or  $< 5.0 /> 7.5 \log_{10}$  CFU/ $\text{cm}^2$  on the skin on the groin) will not be used in the Efficacy Analyses (Section 16.2). This is a common occurrence in clinical-simulation studies. Hence, more subjects will be enrolled and tested to account for test-day baseline failures.

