Two-sided confidence intervals for  $\log_{10}$  CFU/cm^2 changes from baseline will also be calculated. These calculations will use an ANOVA model with subject as a random variable and test substance as a fixed variable. Body area (abdomen or groin) will be a fixed variable. Sample times (30 seconds, 10 minutes, or 6 hours) will be calculated separately using identical models. Differences in  $\log_{10}$  CFU/cm^2 reductions will be calculated based on the same model.

Any deviation(s) from the statistical analysis plan will be described and justified in the final report.

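### No standard-error method is visible for the vehicle contrast; with about 320 active sites against 64 vehicle sites, a default pooled-variance 95% interval is miscalibrated if their residual spreads differ

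*Combined protocol and SAP*

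**What the plan says.** **ATE regression.** The 08/29/2017 amendment adds this to Sections 7.1 and 16.2: post-treatment log10 count is regressed "on the additive effect of a treatment indicator and the baseline or pretreatment measurement". It then says "ATE will be calculated for the 10-minute samples separately for each product and each body area", and a redacted block follows. The criterion against vehicle is that "ZuraPrep™ should be superior to ZuraPrep™ vehicle by a 1.2 margin", judged by "the lower bound of the 95% confidence interval of the ATE of ZuraPrep™ minus the ATE of ZuraPrep™ vehicle".

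**Log-reduction ANOVA.** For intervals on changes from baseline, Section 16.2 says: "These calculations will use an ANOVA model with subject as a random variable and test substance as a fixed variable". It continues: "Body area (abdomen or groin) will be a fixed variable". Each sample time has its own model, so both body areas enter one model. Section 7.3 relies on log-reduction differences at 6 hours to separate active from inactive treatment. Section 16.2 also falls back on log-scale intervals where responder rates are too close to 0% or 100% for approximate methods.

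**Allocation.** Section 11.1 plans at least 320 sites for each active product per body area, while "at least 64 inguinal and abdomen sites will be treated with the negative control".

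**Floor on counts.** Section 13.9: "Colony counts of 0 will be set to 0.5 for further calculation purposes".

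The visible text of either model does not mention unequal variances, robust standard errors or product-specific residual variances. No SD for any product is visible.

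**The concern.** A linear regression or mixed ANOVA with nothing further specified estimates one residual variance and applies it to every product. That is harmless with equal group sizes or equal spreads. Here the groups are 5:1 for each active product against vehicle. The pooled variance is then nearly that of the active products, while the small vehicle group supplies most of the uncertainty in ZuraPrep minus vehicle. If the two spreads differ, the computed standard error is wrong. Left/right pairing is a separate matter, and a random subject term does not repair this.

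At stake are the 1.2 log10 superiority criterion at 10 minutes, the 6-hour log-reduction comparison in Section 7.3, and the Section 16.2 fallback on the log scale. If vehicle residuals vary more than active ones, the lower bound is too high and the margin is passed too often. If they vary less, the interval is needlessly wide and a real effect is harder to show.

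**Working it through.** **1. The plan's own counts (Sections 7.0 and 11.1).** 288 + 32 + 32 = 352 subjects; × 2 = 704 sites per body area. Each active product has 288 + 32 = 320 sites and vehicle has 32 + 32 = 64. All match the plan. With both areas in one ANOVA the counts are 640 per active product and 128 vehicle, the same 5:1 ratio.

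**2. Where each variance comes from.** The active products hold 640/704 = 91% of the sites behind the pooled variance. If spreads are equal, vehicle supplies (1/64)/(1/320 + 1/64) = 0.015625/0.01875 = 83% of the variance of the contrast.

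**3. Formulas.** With residual SDs s_a (active) and s_v (vehicle), independent sites and all three products in one fit:

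- pooled variance s_p² = (638·s_a² + 63·s_v²)/701
- model SE = √[s_p²(1/320 + 1/64)]
- correct SE = √(s_a²/320 + s_v²/64)
- coverage = 2Φ(1.96 × model SE / correct SE) − 1
- one-sided error at the lower bound = (1 − coverage)/2, nominally 2.5%

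The two-product fit (320:64) uses (319·s_a² + 63·s_v²)/382. The SDs are assumptions: s_a = 1 and a range of ratios s_v/s_a.

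**4. One case in full, ratio 1.5.** s_p² = (638 + 63 × 2.25)/701 = 1.112. Model SE = √(1.112 × 0.01875) = 0.1444. Correct SE = √(0.003125 + 0.035156) = 0.1957. The quotient is 0.738, so coverage is 2Φ(1.447) − 1 = 85.2% and the one-sided error is 7.4%.

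**5. The range.** The ANOVA column uses one area's 288/32/32 paired layout, with the subject component at 20% and then 50% of the active-site variance.

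| s_v/s_a | Model SE | Correct SE | Coverage, three-product | One-sided error | Coverage, two-product | Coverage, random-subject ANOVA |
|---|---|---|---|---|---|---|
| 0.5 | 0.132 | 0.084 | 99.8% | 0.1% | 99.7% | 99.5%, 99.0% |
| 0.67 | 0.134 | 0.101 | 99.1% | 0.5% | 98.9% | 98.6%, 98.1% |
| 1 | 0.137 | 0.137 | 95.0% | 2.5% | 95.0% | 95.0%, 95.0% |
| 1.25 | 0.140 | 0.166 | 90.3% | 4.9% | 90.9% | not run |
| 1.5 | 0.144 | 0.196 | 85.2% | 7.4% | 86.8% | 86.5%, 88.0% |
| 2 | 0.154 | 0.256 | 76.2% | 11.9% | 80.0% | 78.1%, 80.7% |

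In the two-product fit the one-sided error at ratio 1.5 is 6.6%. At ratio 0.67 the three-product interval is 0.1335/0.1007 = 1.33 times the correct width; in the ANOVA it is 0.1291/0.1028 = 1.26 or 0.1119/0.0937 = 1.19 times.

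**6. Effect on the lower bound (three-product fit).**

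- Ratio 1.5, s_a = 1: 1.96 × (0.1957 − 0.1444) = 0.10 log10 too high.
- Ratio 1.5, s_a = 0.6 (s_v = 0.9): 0.6 × 0.10 = 0.06 too high. The half-width should be 0.230, not 0.170, so the verdict changes only for an estimate between 1.37 and 1.43.
- Ratio 0.67, s_a = 1: 1.96 × (0.1335 − 0.1007) = 0.06 too low.

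**7. Simulation.** In 4,000 ANCOVAs per case with independent sites, ordinary standard errors covered 85.8% (three products) and 86.1% (two products) at ratio 1.5. HC3 standard errors covered 94.0–95.3% over ratios 0.5 to 2. In the paired 288/32/32 layout, ordinary standard errors covered 86–87% at SDs 0.6/0.9 and 99% at 0.9/0.6. Subject-cluster-robust standard errors gave 94–95% in all cases.

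**The case against.** **The plan does not state a common variance.** This stands. Pooling is the default form of both models, not a written rule. The sentence on calculation by product could be read as separate fits, and the redaction after it may contain the standard-error method. Against that, a treatment indicator needs at least two products in one fit, so single-product regressions do not match the stated model. A two-product fit still covers only 86.8% at ratio 1.5. The Section 7.1 version of the text describes the regression and margins without a visible variance method.

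**The direction is unknown.** This also stands. A reader might infer from the 0.5 rule for zero plates that active counts are compressed against a floor, so that vehicle varies more and the 1.2 margin is passed too easily. The documents do not support that step. They give no SDs and no frequency of zero plates, and kill may vary between active sites more than flora varies between vehicle sites. For the ANOVA the floor can work the other way. A floored active site has a reduction equal to its baseline minus a constant, so it carries the full baseline spread, while much of a vehicle site's baseline cancels. One illustration assumed abdominal baselines uniform over 3.0–5.5 and 35% of active sites at the floor. It gave reduction SDs of 0.66 (active) and 0.56 (vehicle), for which the pooled interval is too wide.

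**The effect is small.** True: it is decisive only near the margin. Section 7.3 sets no numerical margin at 6 hours, so there it matters only for a small difference.

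**Plain HC3 does not suit the design.** This stands too. Each treated body area has a left and a right site on the same subject, and HC3 treats them as independent.

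**Conclusion.** The point holds conditionally. As far as the text is visible, the variance assumption behind the vehicle contrast is left to software defaults, and the 5:1 allocation makes the interval sensitive to that default. At an assumed vehicle/active SD ratio of 1.5, nominal 95% coverage falls to about 85–88% across the regression and ANOVA readings, with a 6–7% false-pass rate at the 1.2 margin instead of 2.5%. At 0.67 the error runs the other way, with coverage of 98–99%. The bound moves by roughly 0.05–0.1 log10 for active SDs of about 0.6 to 1.

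These figures rest on assumed SDs, the minimum site counts and default pooling. They do not show that the superiority test is anti-conservative in this trial, nor that the plan prescribes equal variances. The two-area ANOVA was not run separately; its 640:128 allocation has the same ratio as the one-area layout computed here. The point is still worth acting on because the remedy works in either direction. Moreover, the amendment says it was issued after testing was complete, so an unstated method would be chosen once the data exist.

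**What to change.** Unless the redacted text already does so, add one sentence to Sections 7.1 and 16.2: the ATE regression and its point estimates stay as recommended, and their 95% intervals use heteroscedasticity-robust standard errors clustered by subject. Also say which products enter each fit. Plain HC3 is not enough, because it ignores the left/right pairing.

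In the Section 16.2 ANOVA, keep the random subject term and allow a separate residual variance for each product. The coverage of that version was not simulated here; it is proposed because it removes the equal-variance assumption directly.

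The cost is one sentence per model and a software option, plus a slight loss of precision if the variances are equal. Because testing is complete, record the change and its date, and report the default pooled interval beside it so that a reader can see whether the choice affects the 1.2 criterion.
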